6.13.3 Subgroup Analyses

Further analyses will assess outcomes presented above for subgroups based on demographic, cohort, and disease conditions.

Known-groups analyses comparing various subgroups of interest will provide support for the discriminating ability of the PGI-S items. Analysis of variances (ANOVAs) based on a priori hypotheses will examine mean differences in PGI-S item scores between subjects classified into subgroups, given sufficient subgroup sample sizes ($n \geq 5$):

- It is hypothesized that better PGI-S scores will be observed in WHO Functional Class I subjects compared with WHO Functional Class III subjects.
- It is hypothesized that better PGI-S scores will be observed in Cohort A subjects compared with Cohort B subjects.

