4.2 EXCLUSION CRITERIA

The following will exclude subjects from the study:

1. The subject is known to be pregnant or nursing.
2. The subject has PAH related to any condition not covered under inclusion criteria, including, but not limited to, pulmonary venous hypertension, pulmonary veno-occlusive disease, pulmonary capillary hemangiomatosis, chronic thromboembolic pulmonary hypertension, or other conditions under WHO Group 2, 3, 4, and 5 classifications.
3. The subject has evidence of clinically significant left-sided heart disease (including, but not limited to, left ventricular ejection fraction $<40\%$, left ventricular hypertrophy)

or clinically significant cardiologic conditions, such as congestive heart failure, coronary artery disease, or valvular heart disease.

4. The subject has any form of congenital heart disease (repaired or unrepaired; other than a patent foramen ovale).
5. The subject has any ambulatory or orthopedic limitations that would interfere with the ability to perform the activity.
6. The subject has been hospitalized within 30 days of Screening.
7. Current use of prostacyclin analogs/agonists, except inhaled treprostinil, for the treatment of PAH.
8. Use of any other investigational drug/device, or participation in any investigational study with therapeutic intent within 30 days of Screening (concurrent participation in registry studies is allowed).
9. Any other clinically significant illness that, in the opinion of the Investigator, might put the subject at risk of harm during the study or might adversely affect the interpretation of the study data.

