5.2 ENROLLMENT

The same number of subjects will be enrolled into Cohort A (subjects taking inhaled treprostinil therapy) and Cohort B (subjects who are taking other PAH medications [instead of inhaled treprostinil]). Subjects will be assigned to Cohort A or B based on the use of inhaled treprostinil as determined by the Investigator.

Subjects meeting eligibility criteria will be enrolled into the study and assigned a sequential subject number within their cohort.

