3 STUDY DESIGN

3.1 GENERAL DESCRIPTION

This is an observational, multicenter, single-day, Phase 2 study. This study will include a 14-day Screening Period and a Study Day 1 clinic visit.

Subjects will be required to perform an ISWT to induce symptoms of PAH. The total number of shuttles completed by a subject during the Screening ISWT will be the maximum targeted for that subject during the remaining ISWTs in the study. Subjects' severity of self-reported symptoms of PAH will be measured from pre-activity, immediately after the activity, and through the 30-minute recovery. Subjects will be asked about their PAH symptoms using 3 PGI-S questions that address their overall PAH symptoms, shortness of breath, and physical fatigue.

The subject population includes males and females 18 years and above, with a diagnosis of PAH that is either idiopathic or familial, collagen vascular disease associated PAH, PAH associated with human immunodeficiency virus (HIV) infection, PAH induced by anorexigens/toxins, or PAH associated with repaired congenital systemic-to-pulmonary shunts (repaired ≥ 1 year). Subjects must be World Health Organization (WHO) Functional Class I, II or III and have shortness of breath upon exertion (exhibits a ≥ 1 -point change in Borg dyspnea score). Subjects are permitted to receive Food and Drug Administration (FDA)-approved PAH therapies if on a stable dose regimen for at least 60 days prior to the Screening Visit. Subjects must sign the Informed Consent Form (ICF) prior to participation in any study procedure.

After Screening, subjects will be assigned to 1 of 2 cohorts based on PAH medications as prescribed by their physician; Cohort A will include subjects who are currently prescribed and

using inhaled treprostinil for the treatment of PAH and Cohort B will include subjects who are taking other PAH medications (instead of inhaled treprostinil).

Subjects in Cohort A will be assigned to 1 of 2 sequences:

Sequence 1:

- Period 1: The ISWT will be initiated 3 to 4 hours after a subject's previous dose of inhaled treprostinil (expected trough level). Activity will be timed to allow all procedures, including recovery, to be completed prior to Period 2.
- Period 2: The ISWT will be initiated within approximately 30 minutes of the previous inhaled treprostinil dose (expected peak level). Following recovery and the Investigator's confirmation of return to baseline status, the subjects will be discharged from the study.

Sequence 2:

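### The Cohort A versus Cohort B comparison in SAP 6.13.3 is confounded by prescription and dose timing and cannot count as known-groups evidence for or against the PGI-S

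*SAP*

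**What the plan says.** SAP 6.13.3 states that comparisons of subgroups "will provide support for the discriminating ability of the PGI-S items". ANOVAs "will examine mean differences in PGI-S item scores between subjects classified into subgroups", "given sufficient subgroup sample sizes", which the SAP sets at five or more per group. Two directional hypotheses follow: better scores in WHO Functional Class I than in Class III, and "better PGI-S scores will be observed in Cohort A subjects compared with Cohort B subjects". No covariate, visit, period or time point is named. The population is the PAP, which SAP 6.1 opens to PGI-S or Borg data from any visit.

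Cohort membership is not randomised. SAP 3.1: "After Screening, subjects will be assigned to 1 of 2 cohorts based on PAH medications as prescribed by their physician". Protocol 5.2: "Subjects will be assigned to Cohort A or B based on the use of inhaled treprostinil as determined by the Investigator". Only the peak/trough order within Cohort A is allocated, 1:1 (SAP 3.2.2). Protocol 4.2 excludes "Current use of prostacyclin analogs/agonists, except inhaled treprostinil, for the treatment of PAH", so Cohort B has no prostacyclin-class therapy.

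On Day 1 (SAP 3.1), each Cohort A subject walks once at expected peak, within about half an hour of a dose, and once at expected trough, 3 to 4 hours after a dose. Cohort B walks about 4 hours after its morning PAH dose. Its second walk is timed only from the first one, at least 1 hour later.

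**The concern.** A known-groups test works by comparing groups whose order on the construct is already established, and asking whether the instrument recovers that order. Functional Class I versus III meets this requirement, because it ranks subjects by severity. Use of inhaled treprostinil does not. Users could be less symptomatic because they are treated, more symptomatic because they needed the additional drug class, or similar to non-users.

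If the order is not known, no result can be interpreted. Better scores in Cohort A would be reported as support for the PGI-S, and equal or worse scores as a failure to discriminate. Either could arise from who is prescribed the drug, from when they walked relative to a dose, or from how far they walked, whatever the quality of the items. The result has its own planned table (14.2.3.3), so it will be read as validity evidence.

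**Working it through.** **The plan's own figure.** The documents give no precision or power figure for A versus B. The only design figure (SAP 4, Protocol 10.2) is a 95% interval extending about 0.52 units for a paired change in 36 subjects. The stated inputs give 1.96 × 1.3 / √36 = 0.425, so 0.52 does not reproduce. It concerns a different quantity and plays no part below.

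**Precision of the cohort contrast.**
- Group size: Protocol 5.2 says "The same number of subjects will be enrolled into Cohort A" as into Cohort B. With 36 evaluable subjects, I assume 18 per cohort.
- Half-width = t(0.975, 34 df) × SD × √(2/18) = 2.032 × 0.333 × SD = 0.68 SD.
- At the SAP's item SD of about 2: 1.35 categories. At an assumed SD of 1: 0.68 category.
- An SD of 2 is essentially the maximum for a 1-to-5 item (half the subjects at 1 and half at 5), so 1.35 is close to an upper limit.

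**Case mix (assumed inputs; the documents give none).**
- Shift in the A minus B mean = d × (pA − pB), where p is the proportion in Class III and d is how much worse Class III scores.
- With pA = 0.5 to 0.7, pB = 0.3 and d = 0.5 to 1.0: from 0.5 × 0.2 = 0.10 to 1.0 × 0.4 = 0.40 category, against the hypothesis.
- Exchanging the two mixes gives the same shift in favour of the hypothesis.

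**Simulation of the same mechanism.** Assumptions: 18 per cohort, one PGI-S unit per class, residual SD 1, and class mixes (I/II/III) of 5/40/55% versus 20/50/30%, so mean class differs by 0.4. There were 4,000 runs per scenario. Higher scores are worse, so a negative A minus B favours the hypothesis.

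| True cohort effect | Sicker cohort | Mean A minus B, unadjusted | Significant, A better | Significant, A worse | Mean A minus B, class-adjusted |
|---|---|---|---|---|---|
| 0 | A | +0.40 | 0.1% | 15.7% | 0.00 |
| 0 | B | −0.40 | 15.4% | 0.2% | 0.00 |
| −0.5 | A | −0.10 | 4.0% | 1.4% | −0.50 |
| −0.5 | B | −0.90 | 58.7% | 0.0% | −0.50 |

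Adjustment recovers the truth here only because the simulation makes Functional Class the sole confounder and unaffected by treatment.

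**Dose timing.** Suppose the peak condition lowers PGI-S by e units. Cohort A's mean then falls by e if peak data are used and by 0 if trough data are used. If both are pooled it falls by e/2. Splitting by period does not separate the conditions: in Period 1, Sequence 1 is at trough and Sequence 2 at peak, Period 2 reverses this, and allocation is 1:1. Each period therefore also carries e/2. SAP 6.13.3 does not say which data enter. Screening data would avoid the Day 1 schedule, but no dose timing is set for Screening in either cohort.

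**Exercise load.** Each subject's Day 1 target is capped at that subject's own Screening shuttle count (SAP 3.1), so the stimulus is not equalised between cohorts.

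**The case against.** The strongest reply has five parts.

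- **Known groups are never randomised.** This stands: prescription-based membership is not a defect in itself. The defect is that this grouping has no justified order.
- **The SAP has a rationale, a known inhaled treprostinil effect (6.9, 6.11.3).** This is a visible reason for the direction of the hypothesis. In 6.11.3, however, it is a within-subject contrast of peak with trough. It does not rank users against patients prescribed something else.
- **The consequences are limited.** There is no pass/fail rule, SAP 6.10 marks hypothesis testing as not applicable, and validity also rests on correlations, test-retest reliability and responsiveness. This stands and keeps the point minor.
- **Imbalances will be visible.** SAP 6.7.2 tabulates etiology, Functional Class and background therapy by cohort. SAP 6.12.3 tabulates distance, oxygen use and time since the last PAH dose. This helps a careful reader, but 6.13.3 would still present the contrast as support.
- **Imprecision exceeds the illustrated bias.** At SD 2, a shift of 0.10 to 0.40 is about 7% to 30% of the half-width, and it is below the one-category change that SAP 6.11.1 treats as meaningful. This is fair, although at SD 1 the same shift is about 15% to 59% of the half-width.

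A reader might also infer that the result will reflect case mix instead of discriminating ability. The documents do not support that. They give no case mix for either cohort, and a difference could come from case mix, drug effect, timing, exercise load or a combination.

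**Conclusion.** The point holds as a limit on interpretation. The A-versus-B contrast is confounded by prescription and, on Day 1 data, by dose timing, and no severity ordering justifies its direction. It can neither support nor refute discriminating ability.

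The size and direction of any bias are unknown. The range of 0.10 to 0.40 category and the simulated 15% to 16% of spurious significant results depend on assumed class mixes, an assumed effect per class and 18 subjects per cohort.

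Two stronger inferences should not be drawn. First, the known-groups section as a whole does not fail: the Functional Class contrast does not rest on cohort, and the analyses in 6.11 are untouched. Second, adjusting for Functional Class does not turn the contrast into valid evidence. Class is recorded after at least 60 days of stable therapy, so it may already carry some of the drug's benefit, and it does nothing about dose timing.

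**What to change.** In SAP 6.13.3:

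1. Label the Cohort A versus Cohort B comparison as descriptive and remove it from the known-groups evidence. Keep WHO Functional Class I versus III for that purpose.
2. Name the visit and time point for both comparisons.
3. For Day 1 data, show Cohort A separately for the peak and trough conditions, not by period, each with the difference from Cohort B and its 95% CI.
4. If a model is kept, report the unadjusted difference first. Give a Functional Class-adjusted difference as a sensitivity result, noting that class was recorded on treatment and may absorb part of any drug benefit.

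The cost is a few sentences and a revised shell for Table 14.2.3.3; no new data are needed. Sensitivity to the drug effect remains covered within subject by 6.11.3. The real downside is that one of the two known-groups hypotheses no longer counts as validity evidence, and the other may not be testable. There is no enrolment quota for Class I, and five subjects is 12.5% of 40. If either class falls short of five, the report should say that known-groups validity was not assessed and should not fall back on the cohort contrast.

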6.13.4 Test-retest Reliability

Test-retest reliability will assess the stability of the PGI-S items using data from subjects collected at Baseline. During this 15-minute time interval, subjects are expected to remain relatively stable. The “test” data will be PGI-S item scores at -15 minutes pre-ISWT, and the “retest” data will be PGI-S item scores at 0 minutes pre-ISWT.

Because the PGI-S items are categorical, weighted kappa coefficients will be computed (Streiner and Norman, 1995). Kappa statistics can range from -1 to 1 and are interpreted such that ≤ 0 is poor, >0 to 0.2 indicates slight agreement, 0.21 to 0.4 indicates fair agreement, 0.41 to 0.6 indicates moderate agreement, 0.61 to 0.80 indicates substantial agreement, and 0.81 to 1.00 indicates almost perfect agreement (Landis and Koch, 1977).

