10.3.2 PGI-S Questions Assessment

The primary objective is to characterize the psychometric properties and performance of 3 PGI-S questions (Appendix 15.1) in PAH subjects during pre-ISWT, at the end of activity, and through recovery.

The focus of the analyses will be to describe PGI-S measurement sensitivity of the subjects' self-reported symptoms of PAH at the end of the activity and during recovery from activity. The Sponsor will tabulate symptom scores and compute changes from baseline (pre-activity) scores for each question. Data may be displayed graphically and will be summarized overall and by cohort and sequence/period (as appropriate).

Additionally, for Cohort A, the sensitivity to a known inhaled treprostinil drug effect will be assessed tabulating, across time, the PGI-S measurements with inhaled treprostinil to PGI-S measurements without inhaled treprostinil. Test-retest assessments for PGI-S measurements will be conducted for Cohort B.

Correlations between the 3 PGI-S questions and with Borg dyspnea scores, oxygen saturation, and HR will be assessed. Data for HR recovery at 1 minute after the ISWT will be examined in an exploratory fashion overall and as related to PGI-S measurements.

The onset and recovery profile for activity-induced symptoms will also be characterized.

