- Period 1: The ISWT will be initiated within approximately 30 minutes of the previous inhaled treprostinil dose (expected peak level). Activity will be timed to allow all procedures, including recovery, to be completed prior to Period 2.
- Period 2: The ISWT will be initiated 3 to 4 hours after a subject's previous dose of inhaled treprostinil (expected trough level). Following recovery and the Investigator's confirmation of return to baseline status, the subjects will be discharged from the study.

Subjects in Cohort B will also undergo 2 activity periods:

- Period 1: The ISWT will be initiated approximately 4 hours after the subject's morning dose of PAH medication.
- Period 2: The ISWT will be initiated at least 1 hour following the completion of the previous ISWT. Following recovery and the Investigator's confirmation of return to baseline status, the subjects will be discharged from the study.

The baseline PGI-S and Borg dyspnea score assessments will be conducted prior to (-15 and 0 minutes; pre-ISWT) an activity that is typically expected to induce symptoms of PAH. The subject will initiate activity (ISWT), and these same assessments will be performed immediately at the end of the ISWT (within 1 minute of completing the activity). The PGI-S assessments will also be performed throughout recovery following completion of the ISWT. Continuous pulse oximetry will be performed at each clinic visit starting at each Baseline and through recovery.

The study will consist of the following periods:

Screening: During the Screening Period, subjects who sign the ICF will first undergo all Screening assessments to evaluate eligibility as listed in the inclusion/exclusion criteria. A

window of up to 14 days is permitted to enroll a subject after Screening. When feasible, Screening assessments should be completed on the same day. Rescreening will be allowed with the Sponsor's Medical Monitor approval.

- The ISWT will be performed to determine eligibility and the ability to induce symptoms. Completion of a minimum of 3 shuttles (30 meters) of the test will be required for study eligibility. Pre-ISWT, ISWT conduct, and ISWT recovery will be performed and specific assessments will be conducted as outlined below.

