6.9 ANALYSIS OF ENDPOINTS

The primary objective is to assess the psychometric properties and performance of the PGI-S items.

The focus of the analyses will be to describe the responsiveness to change of the PGI-S items to the subjects' self-reported symptoms of PAH at the end of the activity and during recovery from the activity. The Sponsor will tabulate the relevant symptom scores and compute change from Baseline (pre-activity) scores for each item. Data may be displayed graphically and will be summarized overall and by cohort and sequence/period (as appropriate).

Additionally, for Cohort A, the sensitivity to a known inhaled treprostinil drug effect will be assessed. Tabulations will be made across sequences/periods for the PGI-S measurements with inhaled treprostinil to PGI-S measurements without inhaled treprostinil. Test-retest assessments for PGI-S measurements will be conducted for Cohort B.

Correlations between the 3 PGI-S questions and with Borg dyspnea scores, oxygen saturation, and HR will be assessed. Data for HR recovery at 1 minute after the ISWT will be examined in an exploratory fashion overall and as related to PGI-S measurements.

The onset and recovery profile for activity-induced symptoms will also be characterized.

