6.13 PSYCHOMETRIC ANALYSIS OF THE PGI-S ITEMS

The following analyses will be conducted on the PAP.

6.13.1 *Validity of the PGI-S Items*

A number of specific forms of validity exist, but one of the most important to the present study is construct validity, which describes the relationships among multiple indicators of a construct and the degree to which they follow predictable patterns. Correlations will be computed between PGI-S scores and in Borg Dyspnea scores, oxygen saturation, and HR. The goal is to

demonstrate stronger relationships among measures addressing similar constructs as compared with measures addressing more disparate constructs. Correlations will be computed using data collected at the same or nominally similar time points, specifically, at Baseline (pre-ISWT average of -15 minutes and 0 minutes) and post-ISWT (1, 2, 3, 4, and 5 minutes).

Inferences regarding validity are based on the patterns of correlations among the measures. Cohen (1992) provides the following guideline for interpreting correlation coefficients: absolute values of correlations of 0.50 or greater are considered strong, correlations that fall between 0.30 and 0.49 are moderate, and those between 0.10 and 0.29 are small.

Higher scores on the PGI-S items, Modified Borg scale, and HR indicate worse outcomes, while higher oxygen saturation is a better outcome. Therefore, positive correlations are expected between the PGI-S items and the Modified Borg scale and HR, and negative correlations are expected between the PGI-S items and oxygen saturation. Furthermore, the following are hypothesized:

- The PGI-S Overall item will be at least moderately correlated ($|r| > 0.30$) with oxygen saturation and with HR
- The PGI-S Shortness of Breath item will be at least moderately correlated with the Modified Borg score, oxygen saturation, and HR
- The PGI-S Physical Fatigue item will be at least moderately correlated with oxygen saturation and HR

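### SAP 6.13.4 does not limit the -15 versus 0 minute test-retest kappa to Cohort B, so just-dosed Cohort A peak-walk pairs, where stability is not assured, can enter it

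*SAP*

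**What the plan says.** - **Statistic.** SAP 6.13.4 takes the PGI-S score at -15 minutes as the test, and for the retest "data will be PGI-S item scores at 0 minutes pre-ISWT". It describes the source only as "using data from subjects collected at Baseline", and "weighted kappa coefficients will be computed". It does not state the weights, which visits or periods enter, or how several pairs from one subject are combined.
- **Premise.** The same section says "During this 15-minute time interval, subjects are expected to remain relatively stable".
- **Population.** SAP 6.13 opens with "The following analyses will be conducted on the PAP". SAP 6.1 defines the PAP as anyone with a PGI-S or Borg rating at any visit or time point, so both cohorts are in it. The SAP table list puts Table 14.2.3.4 on the PAP with no cohort limit.
- **Cohort.** Protocol 10.3.2 says "Test-retest assessments for PGI-S measurements will be conducted for Cohort B", and SAP 6.9 repeats it.
- **Dose timing.** For the Cohort A peak period, SAP 3.1 says "The ISWT will be initiated within approximately 30 minutes of the previous inhaled treprostinil dose (expected peak level".
- **Drug effect.** SAP 6.9 says that, for Cohort A, "the sensitivity to a known inhaled treprostinil drug effect will be assessed". No size is given.

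**The concern.** A test-retest coefficient can be read as reliability only if the true state does not move between the two ratings. That is plausible for Cohort B, and for Cohort A at trough. It is less secure when the subject inhaled a dose shortly before the first rating or between the two. A real easing of symptoms in those 15 minutes is scored as disagreement, so the bias from such a change runs one way, toward lower reliability.

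The psychometric properties of the PGI-S are the primary objective, and SAP 6.13.4 attaches verbal grades to kappa. A low pooled or Cohort A value could then reflect measurement error or early response to the dose, and the reader could not tell which. The SAP also leaves open which analysis its Cohort B sentence governs, so two programmers could produce different versions of Table 14.2.3.4 from the same text.

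**Working it through.** The documents state no target or precision for kappa. The sizing figure in SAP section 4 concerns a paired mean change and does not bear on this point.

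**1. Timing of the pair.** If the walk starts t minutes after the dose (t up to about 30), the test rating is at t − 15 and the retest at t:

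| t (min) | Test, min after dose | Retest, min after dose |
|---|---|---|
| 30 | 15 | 30 |
| 15 | 0 | 15 |
| 10 | −5 | 10 |

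The interval therefore lies inside the first half hour after the dose, or straddles the dose.

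**2. Share of peak pairs.** Inputs: 40 subjects (SAP section 4), equal cohorts (Protocol 5.2), and three walks each, with one peak walk per Cohort A subject (SAP 3.1).
- All three walks: 20 / (40 × 3) = 20/120 = 17%
- Day 1 only: 20 / (40 × 2) = 20/80 = 25%
- Cohort A on Day 1: 20/40 = 50%

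With 36 evaluable subjects the shares are the same (18/108, 18/72, 18/36). The counts cover enrolled subjects only. No dose timing is set for the Screening walk, so some Cohort A Screening pairs could also be just post-dose.

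**3. Effect on kappa, latent-scale model.** All inputs here are assumptions. A normal latent score is cut into five categories, with resting distribution 60/28/9/2/1% or 30/40/20/8/2%, test-retest correlation 0.80 to 0.95, and a downward shift of 0 to 1 SD in peak pairs. Pooled table = (1 − f) × stable table + f × peak table. Weighted kappa = 1 − (observed weighted disagreement / chance weighted disagreement).

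| | Linear weights | Quadratic weights |
|---|---|---|
| No peak pairs | 0.55–0.78 | 0.69–0.88 |
| Loss from pooling, f = 1/6 or 1/4, shift 0–1 SD | 0.00–0.12 | 0.00–0.09 |
| Peak pairs alone, shift 1 SD | 0.24–0.29 | 0.36–0.53 |

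The largest pooled loss is 0.78 to 0.66 (30/40/20/8/2%, correlation 0.95, shift 1 SD, f = 1/4). With a shift of 0.25 SD or less the pooled loss is at most about 0.02. With linear weights, the pooled value changes band (0.68 to 0.60, or 0.69 to 0.59) only at correlation 0.90, shift 1 SD and f = 1/4. With quadratic weights it can also cross at smaller shifts when it starts close to 0.81.

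**4. Second model, by hand.** Assumptions: resting distribution 45/35/15/5/0%; 10% of retest ratings land one category away (upward from category 1, evenly split elsewhere); in peak pairs 60% of subjects above category 1 improve by one category. With linear weights, kappa = 1 − (mean absolute difference observed / expected by chance).
- Stable pairs: 1 − 0.100/0.920 = 0.89
- Peak pairs, observed: 0.45 × 0.10 + 0.35 × (0.6 × 0.9 + 0.4 × 0.1) + 0.20 × (0.6 × 1.0 + 0.4 × 0.1) = 0.376
- Day 1 pooled: observed 0.75 × 0.100 + 0.25 × 0.376 = 0.169; kappa = 1 − 0.169/0.903 = 0.81
- All three walks: observed (5/6) × 0.100 + (1/6) × 0.376 = 0.146; kappa = 1 − 0.146/0.909 = 0.84

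Both pooled values stay in the top band (0.81 to 1.00). In Cohort A on Day 1 alone, kappa is 0.84, 0.79 and 0.73 when 20, 40 and 60% improve, so the band drops there from 40% on. With quadratic weights Cohort A stays at 0.83 or above at 10% disagreement. It leaves the top band only at 20% disagreement with 60% improving.

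**The case against.** The strongest reply is that SAP 6.9 and Protocol 10.3.2 already confine test-retest to Cohort B. If that sentence governs 6.13.4, no peak pair enters. It may, however, refer to the Period 1 versus Period 2 comparison in SAP 6.11.2, and 6.13.4, 6.13 and the table list carry no such limit. So it is not established that the plan pools the cohorts, nor that it does not. The conflict lies within the SAP itself, so the statement in SAP section 1 that it supersedes the protocol does not resolve it.

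A reader might also infer that the plan contradicts itself by treating the peak walks as drug-responsive in 6.11.3 and stable in 6.13.4. The documents do not support that. SAP 6.11.3 concerns change from baseline to the end of the walk. A drug can blunt exertional symptoms while resting ratings hold still, and SAP 6.13.2 expects pre-walk symptoms to be minimal, which leaves little room to fall. A resting drug change is a possibility that the plan neither states nor excludes.

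Finally, SAP 6.2 says tables generally show an overall column and one per cohort, so a Cohort B kappa would probably appear anyway, and no pass mark attaches to it. That limits the harm. It does not say which column is the reliability result, and the overall and Cohort A columns could still contain peak pairs.

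**Conclusion.** The point holds in a limited form. SAP 6.13.4 as written can admit Cohort A peak-walk pairs in which 15-minute stability is not assured, and it does not agree with SAP 6.9 and Protocol 10.3.2 on cohort. Any true resting change in those pairs would be scored as unreliability.

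The likely size is modest: peak pairs are 17 to 25% of the pool, and the pooled loss runs from nil to about 0.12. This rests on assumed resting distributions, rating error and drug shift, none of which the documents give. A reader might infer that the reliability grade will fall. A pooled change of band needs a large resting shift or a kappa already near a boundary, and in the second model it appears only within Cohort A on Day 1. The reason to act is that the possible bias is avoidable at little cost.

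**What to change.** In SAP 6.13.4 and Table 14.2.3.4:

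1. Make the main kappa Cohort B pre-walk pairs, and say how this relates to the Cohort B sentence in SAP 6.9 and Protocol 10.3.2 and to the period comparison in 6.11.2.
2. State whether Screening pairs are included. In Cohort B this mechanism does not touch them. State how repeated pairs per subject are handled (for example kappa by walk, or a pooled kappa with an interval that resamples subjects), and state the weights.
3. Show Cohort A trough-walk pairs as supportive.
4. Report Cohort A peak-walk pairs separately, outside the reliability estimate.
5. Treat a Cohort A Screening pair like a peak pair if a recorded inhaled treprostinil dose falls in the same pre-walk window. This depends on that time being available: SAP 6.12.3 tabulates time since the latest PAH medication, which need not be inhaled treprostinil.

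The cost is SAP wording, a filter and precision. Of 120 enrolled pairs, Cohort B keeps 60 over all walks or 40 on Day 1. If pairs were independent with similar spread, the interval would widen by about √(120/60) = 1.41 or √(120/40) = 1.73. Dropping only peak walks would keep 100 pairs (√(120/100) = 1.10), but would not follow the Cohort B statement.
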